3.3.1 Risk Assessment

Table 3.3.1-1: Risk Assessment

Potential Risk of Clinical Significance	Summary of Data/ Rationale for Risk	Mitigation Strategy
Study Intervention(s)		
Interstitial Lung Disease (ILD)/pneumonitis.	MORAb-202 Global Investigator's Brochure (IB)	Eligibility criteria, consistent monitoring (eg, pulse oximetry, signs/symptoms), dosing of MORAb-202 to limit exposure variance in participants with higher body weight, investigator/site training on ILD/pneumonitis detection and management, participant alert card, Safety Committee continuous safety monitoring, ILD Expert Review Committee. These mitigation measures, together with the use of is expected to improve toxicity profile of MORAb-202 and its benefit/risk ratio.
Infusion-related reactions	MORAb-202 Global IB	Premedications for first MORAb-202 infusion, eligibility criteria; close monitoring for hypersensitivity/allergic reactions during MORAb-202 infusions, secondary prophylaxis. Guidelines for management and dose modification are included in Section 7.4.
Aspartate aminotransferase (AST) / alanine aminotransferase (ALT) elevations	MORAb-202 Global IB	Eligibility criteria, monitoring with predose evaluation of liver enzymes at each cycle. Guidelines for management and dose modification are included in Section 7.4.
Nausea	MORAb-202 Global IB	Monitoring at each cycle. Guidelines for dose modification are included in Section 7.4. Management per institutional protocol/investigator discretion.
Ругехіа	MORAb-202 Global IB	Monitoring at each cycle. Guidelines for dose modification and recommended management algorithm is included in Section 7.4. Management or as per institutional protocol/investigator discretion.
Potential reproductive toxicity	MORAb-202 Global IB	Eligibility criteria, pregnancy testing, contraception per Sections 6.1 and 9.2.5, and Appendix 4.

Protocol Amendment No.: 03

Date: 07-Apr-2023

Approved v4.0 930184408 4.0

Table 3.3.1-1: Risk Assessment

Potential Risk of Clinical Significance	Summary of Data/ Rationale for Risk	Mitigation Strategy	
Study Procedures			
Blood draws/use of intravenous catheter for laboratory assessments (eg, pain, bruising, bleeding, infection, fainting)		Per institutional protocol/investigator discretion.	
CT scan/ magnetic resonance imaging (MRI) radiation exposure		Per institutional protocol/investigator discretion.	

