6.1 Inclusion Criteria

Participants are eligible to be included in the study only if all of the following criteria apply:

1) Signed Written Informed Consent

- a) Participants or legally acceptable representatives (LAR, see Appendix 2; where acceptable per local guidelines) must have signed and dated an Institutional Review Board (IRB)/Independent Ethics Committee (IEC)-approved written ICF in accordance with regulatory, local, and institutional guidelines. This must be obtained before the performance of any protocol-related procedures that are not part of normal patient care.
- b) Participants must be willing and able to comply with scheduled visits, treatment schedule, laboratory testing, and other requirements of the study.

2) Type of Participant and Target Disease Characteristics

a) Histologically or cytologically documented metastatic NSCLC AC (as defined by the 8th International Association for the Study of Lung Cancer Classification). ⁶⁰

- b) Not applicable per Protocol Amendment 02
- c) Not applicable per Protocol Amendment 02
- d) Investigator-assessed radiologically documented disease progression during or after last treatment
- e) Measurable target disease assessed by the investigator according to RECIST 1.1.
- f) Lesions that have had external beam radiotherapy (EBRT) or loco-regional therapies such as radiofrequency (RF) ablation must show evidence of disease progression based on RECIST 1.1 to be deemed a target lesion.
- g) ECOG PS of 0 or 1
- h) Resolution of toxicities from prior anticancer therapies to Grade 1 (NCI CTCAE v5.0) severity or lower before administration of study drug except for stable sensory neuropathy (Grade ≤ 2), anemia (hemoglobin [Hgb] ≥ 9.0 g/dL), and long-lasting sequelae (such as alopecia, fatigue) that are not expected to interfere with study treatment.
- i) Not applicable per Protocol Amendment 02
- j) Participants must have received prior treatment, including platinum-based chemotherapy and:
 - i) If without actionable genetic alterations or unknown genetic alterations status, treatment with anti-PD-1/PD-L1
 OR
 - ii) If with known actionable genetic alterations, treatment with at least 1 targeted therapy
- k) Participants must have received no more than 3 prior lines of systemic therapy in the metastatic setting

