6.2 Exclusion Criteria

Participants are excluded from the study if any of the following criteria apply:

1) Medical Conditions

- a) NSCLC histologies other than AC (ie, squamous cell carcinoma, large cell carcinoma).
- b) Not applicable per Protocol Amendment 02
- c) Significant third-space fluid retention (eg, ascites or pleural effusion) that requires repeated drainage.
- d) Clinically significant pericardial effusion requiring drainage.
- e) Prior pneumonectomy. Prior lobectomy and segmentectomy are allowed > 12 months before treatment.
- f) Recent chest radiotherapy. Participants with chest or chest wall radiation may be permitted if chest radiation is documented > 6 months before starting study treatment.
- g) Current infectious pneumonia (including COVID-19-related infection), history of viral pneumonia with evidence of persistent radiologic abnormalities.
 - i) Previous SARS-CoV-2 infection, either suspected or confirmed, within 4 weeks prior to treatment assignment. Additionally, acute symptoms must have completely resolved and based on investigator assessment in consultation with the BMS Medical Monitor

(or designee), there are no sequelae that would place the participant at a higher risk of receiving investigational treatment.

ii) Participants currently in interventional trials for coronavirus disease 2019 (COVID-19), may not participate in BMS clinical studies until the specific washout period is achieved. If a study participant has received an investigational COVID-19 vaccine or other IP designed to treat or prevent COVID-19 prior to screening, enrollment must be delayed until the biologic impact of the vaccine or IP is stabilized, as determined by documented discussion between the investigator and the Medical Monitor (or designee).

NOTE: COVID-19 polymerase chain reaction (PCR) viral testing⁶¹ may be required prior to treatment assignment based on specific country/regional guidelines, and the result of this testing may impact study participation. Testing results should be discussed with the BMS Medical Monitor (or designee) to confirm eligibility.

- h) Investigator assessed current ILD/pneumonitis, or ILD/pneumonitis is suspected at screening or history of ILD/pneumonitis of any severity including ILD/pneumonitis from prior anticancer therapy.

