- m) Clinically significant ECG abnormality, including marked prolonged baseline QTcF (repeated demonstration of a QTcF interval > 500 msec). A history of risk factors for torsade de pointes (eg, heart failure, hypokalemia, family history of long QT Syndrome) or the use of concomitant medications that prolong the QTcF.
- n) Evidence of active bleeding or medically significant hemorrhage within 3 months prior to enrollment.

o) Not applicable per Protocol Amendment 02

- p) Any autoimmune, connective tissue, or inflammatory disorders (eg, rheumatoid arthritis, Sjögren's syndrome, sarcoidosis, etc) where there is documented (or suspicion of) pulmonary involvement. Participants with an active, known, or suspected autoimmune disease. Participants with type I diabetes mellitus, hypothyroidism only requiring hormone replacement, skin disorders (such as vitiligo, psoriasis, or alopecia) not requiring systemic treatment, or conditions not expected to recur in the absence of an external trigger are permitted to enroll.
- q) Concurrent malignancy (present during screening) requiring treatment, or history of prior malignancy active within 2 years prior to treatment assignment, except for the NSCLC under study (ie, participants with a history of prior malignancy are eligible if treatment was completed at least 2 years before treatment assignment and the participant has no evidence of disease). Participants with history of prior early stage basal/squamous cell skin cancer or non-invasive or in situ cancers (ie, superficial bladder cancer, carcinoma in situ of the prostate, cervix, or breast) that have undergone definitive treatment at any time are also eligible.
- r) Any condition including medical, emotional, psychiatric, or logistical that, in the opinion of the investigator, would preclude the participant from adhering to the protocol or would increase the risk associated with study participation or study drug administration or interfere with the interpretation of safety results.
- s) Pulmonary function test (PFT) abnormalities: Forced expiratory volume during first second of forced breath (FEV1) < 70%, or forced vital capacity (FVC) < 60%, and diffusing capacity of the lung for carbon monoxide (DLCO) < 70%.
- t) History of deep vein thrombosis (DVT) within 6 weeks prior to enrollment. Participants who completed at least 2 weeks of anticoagulation prior to starting study treatment and continue while on study are eligible.

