 - i) Participants at risk for DVT secondary to central venous catheters or with past medical history of DVT or clinical symptoms suggestive of DVT must have venous Doppler ultrasonography to rule out DVT during the screening period and prior to initiation of study treatment.

2) Prior/Concomitant Therapy

- a) Participants who have received prior investigational treatment with FR α -targeting agent, or FR α -targeting ADCs including MORAb-202.
- b) Any condition requiring folate supplementation (eg., folate deficiency).
- c) Participants with known intolerance to components of the study drug.

d) Currently enrolled in another clinical study or used any investigational drug or device, which in the opinion of the Sponsor may interfere with the study treatment, within the past 28 days or 5 times the half-life of the investigational drug (whichever is longer) prior to the start of the study treatment.

- e) Any major surgery within 4 weeks of the first dose of study treatment. Participants must have recovered from the effects of major surgery or significant traumatic injury at least 14 days before the first dose of study treatment.
- f) Treatment with any live/attenuated vaccine within 30 days of first study treatment.

3) Physical and Laboratory Test Findings

- a) Evidence of organ dysfunction or any clinically significant deviation from normal in physical examination, vital signs, ECG, or clinical laboratory determinations beyond what is consistent with the target population
 - i) Inadequate renal function as evidenced by calculated creatinine clearance (CrCL) < 50 mL/minute according to a 12- or 24-hour urine collection.
 - ii) Inadequate bone marrow function, as evidenced by:
 - (1) Absolute neutrophil count (ANC) $< 1.0 \times 10^9/L$
 - (2) Hgb < 9.0 g/dL
 - (3) Platelet count $< 75 \times 10^9/L$

NOTE: Supportive therapies as blood/platelet transfusion, hematopoietic stimulating agent including granulocyte colony stimulating factor (G-CSF) formulation needed to achieve the above values are allowed, as per institutional practice, if given ≥ 1 week before study treatment.

- iii) Inadequate liver function, as evidenced by:
 - (1) Total bilirubin > 1.5× upper limit of normal (ULN) except for unconjugated hyperbilirubinemia (eg, Gilbert's syndrome, who must have a total bilirubin < 3× ULN).
 - (2) ALT and aspartate aminotransferase (AST) $> 3 \times$ ULN (in the case of liver metastases $> 5 \times$ ULN).

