7.4.3 Criteria to Resume Treatment

To start the next cycle of MORAb-202 administration, participants must meet the minimum requirements below and be appropriate for additional cycles per investigator judgment:

- ANC $\geq 1000/\mu L$
- Platelet count $\geq 75,000/\mu L$
- All non-hematologic toxicity has resolved to Grade ≤ 1 or baseline.
- All Grade ≥ 3 laboratory abnormalities even if asymptomatic must be corrected to Grade ≤ 1 or baseline
- Meet the requirements for dosing as per management of infusion reactions and ILD/pneumonitis events (Table 7.4.1-1).

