9.2.8 Potential Drug-induced Liver Injury

Wherever possible, timely confirmation of initial liver-related laboratory abnormalities should occur prior to the reporting of a potential drug-induced liver injury (DILI) event. All occurrences of potential DILIs meeting the defined criteria must be reported as SAEs (see Section 9.2.8 and Appendix 3 for reporting details).

Potential DILI is defined as:

- Aminotransferase (AT; ALT or AST) elevation > 3× ULN
- AND
- Total bilirubin > 2× ULN, without initial findings of cholestasis (elevated serum alkaline phosphatase)
- AND
- No other immediately apparent possible causes of AT elevation and hyperbilirubinemia, including, but not limited to, viral hepatitis, pre-existing chronic or acute liver disease, or the administration of other drug(s) known to be hepatotoxic.

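### The transaminase exclusion joins ALT and AST with 'and', so read literally it sets no numeric entry limit on an isolated rise in one enzyme

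*Combined protocol and SAP*

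**What the plan says.** Section 6.2, item 3)a)iii), lists what counts as inadequate liver function. Its second entry takes "ALT and aspartate aminotransferase (AST" as a pair and gives them one shared limit: above 3x ULN, or above 5x ULN in patients with liver metastases.

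Other text bears on how that entry works:

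- **Section 9.2.8**, defining potential drug-induced liver injury, uses the same 3x ULN level but words it as "Aminotransferase (AT; ALT or AST) elevation".
- **Section 6.2, stem of 3)a)**, excludes for "any clinically significant deviation from normal in physical examination, vital signs, ECG, or clinical laboratory determinations" beyond what fits the target population. No enzyme figure is attached.
- **Section 6.2, 1)r)**, lets the investigator exclude for a condition that "would increase the risk associated with study participation or study drug administration".
- **Section 6.1, 2)h)**, requires "Resolution of toxicities from prior anticancer therapies to Grade 1" or lower. It reaches only toxicity left over from earlier cancer treatment.
- **Table 3.3.1-1** names the mitigations for AST/ALT elevations as "Eligibility criteria, monitoring with predose evaluation of liver enzymes at each cycle".
- **Section 7.4.3** requires that Grade 3 or higher "laboratory abnormalities even if asymptomatic must be corrected to Grade ≤ 1 or baseline" before the next cycle.

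**The concern.** In an exclusion criterion the connective decides who is dosed. With a literal 'and', both enzymes must be over the limit before the item applies, so the lower of the two values controls the decision. A patient with one markedly raised transaminase would then face no numeric transaminase limit at entry.

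Two things are at stake. First, transaminase rises are a recognised risk of this drug: Section 3.2.7.1 reports increased ALT in 26.8% and increased AST in 23.2% of Study 101 participants. The risk table relies on eligibility to contain that risk, and this is the only numeric eligibility item on it. Second, sites that read the item differently would decide differently on the same patient. Sections 6 and 9 bar waivers, so a site cannot treat the criterion as approximate.

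A lesser consequence follows under the literal reading only. The resume rule accepts a return to baseline, and for the isolated enzyme that baseline would have no numeric ceiling.

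**Working it through.** The plan has no figure to reproduce, and no sample size or error rate depends on this item. The check is one of logic.

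**1. The two readings.** Let L be the limit: 3x ULN, or 5x ULN with liver metastases.

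- Literal: exclude if ALT > L and AST > L, that is, if min(ALT, AST) > L.
- Per enzyme: exclude if ALT > L or AST > L, that is, if max(ALT, AST) > L.

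| ALT > L | AST > L | Literal | Per enzyme |
|---|---|---|---|
| no | no | not excluded | not excluded |
| yes | no | **not excluded** | **excluded** |
| no | yes | **not excluded** | **excluded** |
| yes | yes | excluded | excluded |

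The readings differ exactly in the two isolated-rise rows. In those rows the literal form puts no upper bound on the raised enzyme.

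**2. Illustrative patients.** The enzyme values are assumed; they are not in the documents.

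| Case | L | ALT | AST | Literal | Per enzyme |
|---|---|---|---|---|---|
| (a) no liver metastases | 3x | 4x | 2x | 2 ≤ 3, not excluded | 4 > 3, excluded |
| (b) liver metastases | 5x | 7x | 4x | 4 ≤ 5, not excluded | 7 > 5, excluded |
| (c) no liver metastases | 3x | 4x | 3.5x | 3.5 > 3, excluded | 4 > 3, excluded |

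**3. Is there another numeric limit?** Sections 6.1 and 6.2 contain no other ALT or AST figure. The bilirubin, alkaline phosphatase and albumin limits are separate items on other analytes. What remains is the 3)a) stem and 1)r), both matters of judgement, and 2)h), which does not reach a rise caused by, for example, liver metastases.

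**4. Does the document settle the reading?** The signals conflict.

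- Towards per enzyme: exclusion 1)e) uses 'and' distributively ("Prior lobectomy and segmentectomy are allowed" plainly means either operation).
- Towards literal: Section 9.2.8 uses 'or' when either enzyme is to suffice. Exclusion 1)s) uses both 'or' and 'and' between lung-function thresholds, which invites a reader to give them different meanings.

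**5. Resume threshold.** Take baseline to be the eligibility value (an assumption). Under the literal reading, the baseline level to which ALT must return is 4x ULN in case (a), against at most 3x under a per-enzyme limit. In case (b) it is 7x, against at most 5x. Other rules contain this. Table 7.4.1-1 generally requires a one-level dose reduction after a Grade 3 or higher laboratory abnormality. Section 7.4.2 requires Medical Monitor consultation before a reduction and allows only one. Section 8.1 requires stopping if the investigator judges that continuing is not in the participant's best interest.

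**The case against.** The best counter-argument is that the intended meaning is clear enough. The item sits under a heading about evidence of inadequate liver function, and one limit shared by two tests is a natural reading. The Amendment 02 change log in Appendix 8 supports this: alkaline phosphatase was moved out of this same item into its own, and the stated reason was clarity. Had the item been conjunctive, that move would have tightened eligibility in substance. The superseded sentence is not shown, so this is evidence of intent and not proof.

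It can also be said that the DILI definition is a reporting rule that further requires raised bilirubin and no other apparent cause, and so is not an entry standard. The judgement clauses still allow an investigator to turn away a patient with an isolated rise, and enzymes are checked before each cycle. Nothing in the documents shows that any site has misread the item.

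Most of this stands. The per-enzyme reading is probably intended, the DILI wording shows only that the drafting is inconsistent, and the risk is partly contained. It does not remove the point. Probable intent does not correct the words of a binding criterion, discretionary clauses do not give sites a common rule, and on-treatment checks do not decide who enters.

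**Conclusion.** The concern holds as a drafting ambiguity of modest weight in an operative safety criterion. Followed literally, exclusion 3)a)iii)(2) leaves an isolated rise in ALT or AST without a numeric limit at entry, although the plan counts eligibility among its mitigations for such rises. The disagreement between readings is confined to patients with one enzyme above the limit and the other at or below it. How many there would be cannot be worked out from the documents. The effect on the resume threshold is secondary: it depends on the literal reading and on baseline meaning the eligibility value, and the dose-modification and stopping rules limit it. No bias in response rate or any other efficacy estimate is claimed.

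**What to change.** Reword Section 6.2, 3)a)iii)(2), so that it excludes for ALT **or** AST above 3x ULN (above 5x ULN in the case of liver metastases). Either enzyme over its limit then excludes, and the connective matches Section 9.2.8. Make the same change in any eligibility checklist that sites use at screening; the protocol itself mentions only a screening log. The cost is one word, the matching site material, and possibly a few more screen failures at sites that now apply the literal reading.

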6.3 Lifestyle Restrictions

Not applicable. No restrictions are required.

6.4 Screen Failures

Screen failures are defined as participants who consent to participate in the clinical study but who are not subsequently assigned to treatment in the study/included in the analysis population.

A minimal set of screen failure information is required to ensure transparent reporting of screen failure participants, to meet the Consolidated Standards of Reporting Trials (CONSORT) publishing requirements, as applicable, and to respond to queries from regulatory authorities. Minimal information includes date of consent, demography, screen failure details, eligibility criteria, and any serious AEs.

6.4.1 Retesting During Screening or Lead-in Period

Participant re-enrollment: This study permits the re-enrollment of a participant who has discontinued the study as a pretreatment failure (ie, participant has not been assigned to treatment/has not been treated). If re-enrolled, the participant must be reconsented and will be issued a new patient identification number.

Retesting of laboratory parameters, PFTs and/or other assessments within any single screening visit will be permitted (in addition to any parameters that require a confirmatory value).

Protocol Amendment No.: 03

The most current result prior to treatment assignment is the value by which study inclusion will be assessed, because it represents the participant's most current clinical state.

Laboratory parameters and/or assessments that are included in Table 2-1, Screening Procedural Outline, may be repeated in an effort to find all possible well-qualified participants. Consultation with the Medical Monitor may be needed to identify whether repeat testing of any particular parameter is clinically relevant.

7 STUDY INTERVENTION(S) AND CONCOMITANT THERAPY

Study intervention is defined as any investigational intervention(s), marketed product(s), placebo, procedure(s), or medical device intended to be administered to a study participant according to the study protocol. Study intervention includes both Investigational [Medicinal] Product (IP/IMP) and Non-investigational/Auxiliary [Medicinal] Product (Non-IP/Non-IMP/AxMP) as indicated in Table 7.1-1.

An IP, also known as IMP in some regions, is defined a pharmaceutical form of an active substance or placebo being tested or used as a reference in a clinical study, including products already with a marketing authorization but used or assembled (formulated or packaged) differently from the authorized form, or used for an unauthorized indication, or when used to gain further information about the authorized form.

Other medications used as support or escape medication for preventative, diagnostic, or therapeutic reasons, as components of the standard of care for a given diagnosis, may be considered as IPs/AxMPs.

